# 7 Design of the randomized controlled trial

# 7.1 Statement of design and randomisation

This is a prospective, randomized multi-centre study in adult and paediatric subjects from Australia, with type 1 diabetes mellitus aged 12 – 25 years. Participants can be on CSII or MDI treatment regimens to be eligible. After a run-in phase, subjects will be randomly assigned to one of the following two arms:

HCL arm: MiniMedTM 670G for 6 months; OR Conventional arm: MDI or CSII for 6 months.

Randomization will be stratified based on 4 variables: Time spent in target sensor glucose range (3.9 – 10mmol/L) – with participants evenly split above and below 55%(17) time in target range, age, diabetes duration, and centre site. This will be managed by the Clinical Trials Centre in Sydney.

# 7.2 Sample size determination and power calculations

## Study Subjects:

Children, adolescents and adults with T1DM aged between 12 and less 25 years with diabetes duration of at least 1 year and c-peptide <0.1 nmol/L, HbA1c <10.5% and on insulin pump therapy for at least 3 months OR multi-daily injections (≥4 per day) will be eligible for the trial. Inclusion and exclusion criteria are expanded upon below.

# Sample size:

Sample size is computed for a parallel design RCT with 2 groups comparing a hybrid closedloop system with usual care in individuals with type 1 diabetes with HbA1c <10.5%; with time in range 3.9 - 10mmol/L at 6 months as primary outcome. Sample size is computed for a paediatric study age 12-<25 years old.

To estimate the total sample size, data from the JDRF CGM RCT were used(17). There were N=97 12-<25 years of age, who used injections or pumps at enrolment, had a baseline HbA1c value <10.5%, were randomized to the control group (usual care), and had blinded CGM data at randomization and at 6 months. The confidence interval for the effective SD (after adjusting for baseline) was 15% for the younger group.

Assuming parallel groups, normal distribution for the treatment effect, a 1:1 allocation, a 2tailed test with null hypothesis stating that the difference is zero, no corrections for multiple comparisons, and a type I error = 5%, the following total sample size is required:

> To detect a 10% difference, using an SD of 13%, and 85% power, 64 subjects are required in each arm. Allowing for 20% predicted drop-out, 80 subjects will be enrolled to each arm (160 total participants).

This study is also powered to detect a difference in time spent in the hypoglycaemic range (<3.9mmol/L) using the same JDRF CGM RCT data. Since time below 3.9mmol/L at 6 months

is not normally distributed, its mean was estimated using a robust procedure. On the other hand, since differences in time below 3.9mmol/L from randomization to 6 months are normally distributed, the SD and the effective SD were estimated using the raw/untransformed data. The two point estimate and 95% CI confidence intervals for the effective SD 6% (95% CI: 5% to 7%). The estimated robust (MM estimate that down-weights outliers means for % time below 3.9mmol/L at 6 months is 5.7%.

The required total sample size (assuming parallel groups, normal distribution for the change in treatment effect, a 1:1 allocation, a 2-tailed test with null hypothesis stating that the difference is zero, no corrections for multiple comparisons, and a type I error = 5%) is:

• 12-<25 years: **100 participants** required to detect a 60% reduction in time spent <3.9mmol/L (using a 6%SD and 80% power). This is less than the 160 recruitment target to demonstrate an improved time spent in range.

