## 1. Glycaemic(24hr, day (0600 – 2400), night (0000 – 0600))

CGM data will be collected in three time blocks; baseline (3 weeks CGM), 13 weeks (2 weeks CGM) and 26 weeks (3 weeks CGM) post randomisation. A sub analysis of HCL vs. MDI and HCL vs. CSII is planned.

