## 6. Biomarkers (all ages)

Assess the difference between MiniMedTM 670G Insulin Pump Hybrid Closed Loop System vs standard therapy (MDI and CSII) after 6 months of treatment on the following biomarkers:

- Cell Adhesion Molecules (CAM)S i.
- ii. Soluble vascular cell adhesion molecules sVCAM
- Soluble intercellular adhesion molecules sICAM iii.
- s-e Selectin iv.
- Oxidized Low density lipoprotein v.
- Myeloperoxidase. vi.
- MicroRNA signatures for arterial, renal and retinal complications vii.
- viii. **Telomerase**
- DNA methylation/acetylation ix.
- Glycomark Χ.
- Isoprostanes and proteomics xi.
- Clotting profile xii.

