# 7.3 Statistical Analysis

All statistical analyses will be performed using SAS for Windows (SAS Institute Inc) and STATA (StataCorp). The analysis population will be the intention-to-treat population, which will be defined as all participants who are randomised and have at least 1 visit after baseline. P-values <.05 will be considered statistically significant and 2-sided P-values will be reported. Descriptive statistics will be used to characterize participants at study entry

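### Two hypotheses are powered, every P below .05 counts as significant, and no testing order is set: a fixed sequence would hold the pair at 5% at little cost in power.

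*Protocol*

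**What the plan says.** Section 5 states two quantified hypotheses: a 10% gain in time in range 3.9–10 mmol/L and a 60% reduction in time below 3.9 mmol/L. Section 6.3.1 makes time in range the only primary endpoint.

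Section 7.2, under the sample size heading, powers the trial for time in range and then adds: "This study is also powered to detect a difference in time spent in the hypoglycaemic range". That second outcome has its own effect, SD, power and total of 100. Both calculations take a 5% type I error, two-sided testing, "a 1:1 allocation" and "no corrections for multiple comparisons".

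Section 7.3 gives the decision rule: "P-values <.05 will be considered statistically significant and 2-sided P-values will be reported". The sentence is not limited to the primary endpoint. Nothing in 7.2 or 7.3 ranks the two powered outcomes, divides alpha between them or makes one test conditional on the other. The closing part of 7.3 labels only subgroup and additional analyses as exploratory.

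**The concern.** An outcome with its own hypothesis, effect size and power statement will be read as confirmatory. Under the blanket .05 rule, a significant result for time below 3.9 mmol/L could be claimed whether or not time in range succeeds, so the trial has two chances at a headline claim and each uses the full 5%.

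The hypoglycaemia claim is the one at stake. As written, it has no defined relation to the primary test, and a P of .04 on it carries the same formal status as a P of .04 on any other secondary outcome tested under 7.3.

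**Working it through.** **Inputs, all from section 7.2.**
- Time in range: difference 10 points, SD 13 (an SD of 15 is also given there), 85% power, 64 per arm.
- Time below 3.9 mmol/L: control mean 5.7%, reduction 60%, so a difference of 0.6 × 5.7 = 3.42 points; SD 6 (95% CI 5 to 7); 80% power; total 100.
- Two-sided alpha .05; 80 enrolled per arm and 20% dropout, so 80 × 0.8 = 64 completers per arm.

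**1. The plan's own figures.** Per-arm n = 2 × (z_alpha/2 + z_power)² × SD² / difference².
- Time below 3.9: 2 × (1.960 + 0.842)² × 36 / 3.42² = 48.3, so 49 per arm or 98 in total. The noncentral t gives 50 per arm, 100 in total. The stated 100 reproduces.
- Time in range: 2 × (1.960 + 1.036)² × 169 / 100 = 30.3, so 31 per arm (32 by t, 64 in total). The stated 64 matches a total, not a per-arm number. This matters below because the cost of a sequence depends on the primary power.

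**2. Error across the two powered hypotheses.** If neither effect exists and the tests are independent, the chance of at least one P below .05 is 1 − 0.95² = 0.0975. With assumed correlations of 0.3 and 0.6 between the test statistics it is 9.5% and 8.8%. If time in range truly improves, only the hypoglycaemia null can be falsely rejected, and that error is 5% with or without a sequence. The excess therefore arises when the primary hypothesis is also null.

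**3. Error under a fixed sequence.** If both nulls hold, a false hypoglycaemia claim needs a false primary claim first, so the chance of any false claim is that of the first test, 5%.

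**4. Power at 64 completers per arm (noncentral t).**

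| Outcome | Difference | SD | Power |
|---|---|---|---|
| Time in range | 10 | 13 | 99.1% |
| Time in range | 10 | 15 | 96.3% |
| Time below 3.9 | 3.42 | 6 | 89.2% |
| Time below 3.9 | 3.42 | 7 | 78.3% |

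**5. Cost of the sequence.** Power for the hypoglycaemia claim becomes the probability that both tests succeed. Under independence:
- Primary SD 13: 0.991 × 0.892 = 0.884, a loss of about 1 point.
- Primary SD 15: 0.963 × 0.892 = 0.859, a loss of about 3 points.
- Primary power truly 85%: 0.85 × 0.892 = 0.758, about 76%.

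A normal approximation over assumed correlations from −0.3 to 0.6 gives 88.9% to 89.4% (SD 13), 86.3% to 88.0% (SD 15) and 75% to 80% (primary power 85%), against 89.7% unadjusted on the same approximation.

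**The case against.** The strongest reply is that "no corrections for multiple comparisons" appears only in the lists of sample-size assumptions. A reader might infer that the protocol has adopted a policy of uncorrected testing. The documents do not support that: section 7.3 contains no such statement. Testing order is also often left to a statistical analysis plan, and one may exist that is not shown. Both points stand. What remains is the unrestricted .05 rule in 7.3 alongside a second outcome that the protocol itself calls powered; an analysis plan that ranked the two would be narrowing a rule the protocol states without limit.

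It is also true that time in range is the sole primary endpoint, so the primary claim's type I error stays at 5%. Time below 3.9 mmol/L is named in advance with a stated effect, so it is not just one chance finding among many.

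A reader might go further and count every glycaemic measure in each time-of-day window, the planned comparisons with each control regimen ("A sub analysis of HCL vs. MDI and HCL vs. CSII is planned"), the questionnaires and the biomarker panels as one large confirmatory family in which false positives are certain. The documents do not support this. Section 7.3 lists time-of-day effects, time in various glycaemic ranges and differences by control regimen among its exploratory analyses, and treats several other outcomes descriptively. The glycaemic measures overlap heavily, so treating them as independent overstates the error. Nor can all of them be null once time in range improves, because time below, within and above range sum to 100%. For the biomarkers, no analyte count or panel-level test is given from which an error rate could be computed.

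Finally, the low cost of a sequence rests on a primary power well above the stated 85%. That is correct, and the case of a true 85% is therefore shown.

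**Conclusion.** The point holds for the two powered hypotheses. The protocol states no order between them and lets each be claimed at .05. The chance of at least one false claim is up to 9.75% under the joint null with independent tests, and lower with correlation; the primary claim on its own remains at 5%. A fixed sequence brings the pair to 5%.

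The small power cost assumes 64 completers per arm and the protocol's own differences and SDs. Hypoglycaemia power then stays at about 86% to 88%, above the planned 80%. Two conditions would take it below 80%: a true primary power of only 85% (about 76% with the sequence), or an SD of 7% for time below 3.9 mmol/L, the upper limit given in 7.2 (about 78% even without the sequence). If the trial were reduced to the 32 per arm that the time-in-range inputs need, the hypoglycaemia outcome would miss its own requirement of 50 per arm whatever the testing order.

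This is an improvement worth making, not a flaw in the primary analysis.

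**What to change.** In section 7.3, limit the .05 rule and state the order: test time in range 3.9–10 mmol/L at two-sided .05; test time below 3.9 mmol/L at two-sided .05 only if the first test is significant; describe P-values below .05 on other secondary outcomes as not adjusted for multiplicity and supportive.

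This is a change of wording only. The primary test and the sample size are untouched. The price is that the hypoglycaemia claim depends on the primary succeeding, which costs about 1 to 3 points of power on the protocol's inputs. By comparison, testing hypoglycaemia at a Bonferroni level of .025 would give 83.7% against 89.7% unadjusted (normal approximation), and would also tighten the primary test.

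### The primary sample-size statement does not reproduce: its inputs need 32 per arm, not 64, for 85% power, and the SD behind it is unclear

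*Protocol*

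**What the plan says.** Protocol section 7.2, under Sample size, sizes the trial on time in range 3.9–10 mmol/L at 6 months. It assumes "a 1:1 allocation, a 2tailed test with null hypothesis stating that the difference is zero", with "no corrections for multiple comparisons, and a type I error = 5%, the following total sample size is required". The result follows: "To detect a 10% difference, using an SD of 13%, and 85% power, 64 subjects are required in each arm". Twenty per cent drop-out raises this to 80 per arm, 160 in all.

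Just before, the section describes the data from an earlier CGM trial from which the variability was taken: "The confidence interval for the effective SD (after adjusting for baseline) was 15% for the younger group". No other SD for time in range appears before the calculation uses 13%.

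A second calculation covers time below 3.9 mmol/L. It takes a mean of 5.7%, a 60% reduction, an SD of 6% (95% CI 5% to 7%) and 80% power, and arrives at 100 participants. The section then remarks: "This is less than the 160 recruitment target to demonstrate an improved time spent in range".

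**The concern.** Every input to a standard two-group calculation is stated, so the result can be checked, and it does not come out. A standardised difference of 10/13 is large, and 64 per arm is far more than 85% power needs at that effect size.

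The SD adds a second problem. One number cannot be a confidence interval, so the reader cannot tell whether 15% is the estimate, a limit of an interval, or something else, nor where 13% comes from.

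At stake is the accuracy of the justification for randomising 160 young people to a device trial. A reader of section 7.2 would believe the trial has 85% power for 10 points when it has considerably more, and could not tell which SD the design rests on.

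**Working it through.** **Inputs (all from section 7.2).** Difference 10 percentage points; SD 13%; two-sided 5%; 85% power; 1:1 allocation; no multiplicity correction; 20% drop-out. Alternative SD: 15%.

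**1. The stated requirement.** Normal approximation, per arm:

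n = 2 (z₀.₉₇₅ + z₀.₈₅)² SD² / Δ² = 2 × (1.960 + 1.036)² × 13² / 10² = 2 × 8.978 × 1.69 = 30.3, so 31.

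The two-sample t-test gives 31.3, so **32 per arm, 64 in total**. The protocol states 64 per arm, 128 in total. The figure is not reproduced.

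**2. The same at SD 15%.** 2 × 8.978 × 2.25 = 40.4, so 41; the t-test gives 41.4, so **42 per arm, 84 in total**. This does not give 64 per arm either.

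**3. Power the design has (t-test, 10 points).**

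| Evaluable per arm | SD 13% | SD 15% |
|---|---|---|
| 32 | 85.7% | 74.7% |
| 64 | 99.1% | 96.3% |

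**4. What 64 per arm would match at 85% power.** The t-test needs a standardised difference of 0.534. For 10 points that means an SD of 10/0.534 = 18.7%, which appears nowhere in the protocol. Equivalently, the detectable difference is 0.534 × 13 = 6.9 points, or 0.534 × 15 = 8.0 points.

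**5. Other readings tried at SD 13% and 85% power (per arm, normal approximation unless noted).** One-sided 5%: 25. Two-sided 2.5%: 37. Two-sided 1%: 45. Inflation for a rank test: 33 to 36. An SD of 13% × √2, as for an unadjusted change score with no correlation: 61 (t-test 62). The last comes closest but still misses 64, and the section describes its SD as already adjusted for baseline.

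**6. Drop-out.** 64 / 0.80 = 80 per arm. This step is correct.

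**7. Hypoglycaemia check.** Δ = 0.60 × 5.7 = 3.42 points; SD 6%; 80% power. The t-test gives 49.3, so 50 per arm and 100 in total. The stated figure reproduces, as a total and before drop-out. With 20% drop-out it becomes 100 / 0.80 = 125 enrolled. The section's closing remark therefore compares a number before drop-out (100) with one after it (160).

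**The case against.** The strongest reply is that the error is harmless: it runs in the safe direction, and the difference to be detected, the test, alpha and enrolment all stay as they are. This stands, and it limits the point to a wrong justification.

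Four stronger readings are tempting, and the document does not support them.

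- **That a total was mislabelled as a per-arm figure.** The lead-in "the following total sample size is required" and the exact match to 64 in total suggest it, and the hypoglycaemia figure is a total. But the origin is not stated. Another account also fits: the protocol plans HCL versus MDI and HCL versus CSII comparisons, and if regimens split evenly (an assumption), 64 per arm leaves 32 against 32 within each regimen, with 85.7% power at SD 13%. The protocol does not say the trial was sized that way, so this does not rescue the sentence, but the authors should give the origin.
- **That the calculation used a smaller SD than its source reported.** The sentence carrying 15% is garbled; 15% could be an upper limit around an estimate of 13%. Only the lack of clarity, and the unexplained 13%, can be asserted.
- **That 160 cannot be justified by either objective.** At the point estimates, time in range needs 64 / 0.80 = 80 enrolled (SD 13%) or 84 / 0.80 = 105 (SD 15%), and hypoglycaemia 125. But at the protocol's own upper limit of 7% for the hypoglycaemia SD, the requirement is 67 per arm (t-test 66.7), 134 evaluable, and 134 / 0.80 = 167.5, so about 168 enrolled. The protocol does not argue this, yet 160 is not indefensible on its figures.
- **That the DSMB would be misled.** Its terms of reference include monitoring the sample-size assumptions, but no re-estimation procedure or decision is tied to the figure.

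**Conclusion.** The primary sample-size statement is wrong as written. On its own inputs the requirement is 32 per arm (64 in total), half the number stated; 64 evaluable per arm gives about 99% power rather than 85%. If the SD is 15%, the requirement is 42 per arm and the power at 64 is about 96%. The description of the SD is also defective: a single number is called an interval, and the use of 13% is unexplained.

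The error is conservative. The trial is not underpowered for its primary endpoint at either SD, and nothing here calls for a change in enrolment. These results assume a two-sample comparison with a normally distributed outcome, an SD that already reflects baseline adjustment, as the section says, and drop-out no worse than 20%.

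**What to change.** Keep 160 enrolled and reword section 7.2:

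- State that 32 per arm (64 in total) gives 85% power for 10 points at SD 13%, and that 42 per arm would be needed if the SD is 15%.
- Say what the 15% is (estimate or limit), give the actual interval, and name the SD that is the design assumption.
- State what 160 enrolled provides with 20% drop-out, that is, 64 evaluable per arm: about 99% power for 10 points at SD 13% or 96% at SD 15%; or, equivalently, 85% power for 6.9 or 8.0 points.
- If 64 per arm was chosen for another reason, say so.
- Compare the hypoglycaemia requirement on one basis: 100 evaluable against 128 evaluable, or 125 enrolled against 160 enrolled, at SD 6%.

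The cost is a rewording of one section, with no change to enrolment or analysis.

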# 7.3 Statistical Analysis

All statistical analyses will be performed using SAS for Windows (SAS Institute Inc) and STATA (StataCorp). The analysis population will be the intention-to-treat population, which will be defined as all participants who are randomised and have at least 1 visit after baseline. P-values <.05 will be considered statistically significant and 2-sided P-values will be reported. Descriptive statistics will be used to characterize participants at study entry

# Primary endpoint

The primary endpoint, average % time spent in target glycaemic range (sensor glucose level 3.9 - 10 mmol/l) during 6 months, will be analysed using Analysis of covariance (ANCOVA) adjusting for baseline percentage score and site. Least square means and least square mean differences and their associated 95% confidence intervals will be presented for each treatment group and between groups. In the event that data are not normally distributed the Mann–Whitney–Wilcoxon (Wilcoxon Rank-Sum) Test will be employed which tests the medians. In addition if data are skewed, bootstrap methods(21) will be used which allows for a non-parametric test of the arithmetic means. Bootstrap methods simply estimate the distribution of the statistic through resampling with replacement (many times) from the original data population. These methods will also be employed for average % CGM as outlined in the secondary objectives.

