Study Design	HCL vs. standard therapy (MDI and CSII), Australian multicentre parallel design study.  Participants will be randomized to use HCL or continue on standard therapy( MDI and CSII)  Minimisation randomisation will be employed, stratifying by time in target glucose range 3.9-10 mmol/L, age, diabetes duration, and centre site.							

	Duration of study – 7 months							
	Enrolment period – 12 months							
Investigational device	MiniMed™ 670G Insulin Pump Hybrid Closed Loop System.							
Hypothesis	1. HCL will increase time in sensor glucose target range (3.9 –							
	10mmol/L) compared to standard therapy.							
	2. HCL will reduce time spent in hypoglycaemic range							
	(<3.9mmol/L) compared to standard therapy.							
	3.HCL will improve glycaemic control as assessed by HbA1c.							
	4. HCL will have a positive impact on quality of life and fear of							
	hypoglycaemia as determined by participant/parent questionnaires							
	5. HCL will be a cost effective intervention for the management of							
Duimour abiactiva	type 1 diabetes compared to standard treatment.  1. The primary objective is to compare the proportion of time							
Primary objective	spent in target glycaemic range (sensor glucose level 3.9 - 10							
	mmol/l) while using HCL or using standard therapy (MDI and							
	mmol/l) while using HCL or using standard therapy (MDI and CSII).							
Secondary objectives	The secondary objectives are to compare the efficacy of the							
٠٠٠٠	MiniMed™ 670G Insulin Pump Hybrid Closed Loop System							
	versus standard therapy (MDI and CSII) by the measurement of							
	the following:							
	1.Glycaemic(24hr, day (0600 – 2400), night (0000 – 0600))							
	CGM data will be collected in three time blocks; baseline (3 weeks							
	CGM), 13 weeks (2 weeks CGM) and 26 weeks (3 weeks CGM)							
	post randomisation. A sub analysis of HCL vs. MDI and HCL vs.							
	CSII is planned.							
	i. CGM data:							
	a. % CGM Time <2.8 mmol/L							
	a. % CGM Time <2.8 mmol/L b. % CGM Time <3.3 mmol/L							
	c. % CGM Time <3.9 mmol/L							
	d. % CGM Time 3.9-7.8 mmol/L							
	e. % CGM Time >10.0 mmol/L							
	f. % CGM Time >13.9 mmol/L							
	g. % CGM Time >16.7 mmol/L							
	h. Standard Deviation and Coefficient of Variation							
	of CGM values							
	i. Mean CGM glucose							
	ii. Average Fasting blood glucose (mmol/L), as measured							

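### The primary ANCOVA gives way to an unadjusted rank-sum test, wrongly said to test medians, if the data look non-normal; the model also omits two of the four minimisation factors

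*Protocol*

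**What the plan says.** **Allocation.** The Synopsis (Study Design) says: "Minimisation randomisation will be employed, stratifying by time in target glucose range 3.9-10 mmol/L, age, diabetes duration, and centre site". Section 7.1 repeats the four factors, "time in target range, age, diabetes duration, and centre site", and splits time in range at 55%.

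**Primary model.** The primary endpoint paragraph of section 7.3 says the outcome "will be analysed using Analysis of covariance (ANCOVA) adjusting for baseline percentage score and site". Least-squares means and their differences are to be given with 95% confidence intervals. Age and diabetes duration do not appear.

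**Fallbacks.** The same paragraph says that, if the data are not normally distributed, the Wilcoxon rank-sum "Test will be employed which tests the medians". It then adds: "In addition if data are skewed, bootstrap methods(21) will be used which allows for a non-parametric test of the arithmetic means". No covariates are named for either method. The same rules are extended to the secondary CGM percentages.

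**Target and sample size.** Section 6.2.1 sets the objective as a comparison of the proportion of time in range, and section 5 expects a 10% increase. Section 7.2 reports an effective SD of 15% after adjustment for baseline. It then plans with a 10% difference, SD 13%, 85% power and a two-sided 5% test, and states 64 per arm, or 80 per arm after 20% drop-out.

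**The concern.** The switch changes three things at once: the hypothesis, the effect measure and the adjustment.

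- **Hypothesis.** The rank-sum test asks whether a random value from one arm tends to exceed one from the other. That is a comparison of medians only if the two distributions have the same shape and differ by a shift. A closed-loop system may well change the spread and the tails of time in range as well as its centre.
- **Effect measure.** The rank-sum test gives no difference in percentage points, which is what the objective and hypothesis are about.
- **Adjustment.** Baseline time in range, probably the strongest predictor of the outcome, is discarded together with site.

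The trigger is also misplaced. ANCOVA asks for roughly normal residuals rather than normal raw data, and with about 64 per arm inference on a mean difference tolerates moderate departures.

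A lesser issue is the covariate list. Minimisation balances the arms on age and diabetes duration. If these predict outcome and the model ignores them, the standard error does not reflect that balance and is too large.

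**Working it through.** **1. The plan's own figure.** Inputs from section 7.2: difference 10, SD 13, power 85%, two-sided 5%.

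n per arm = 2 × (1.960 + 1.036)² × 13² / 10² = 2 × 8.98 × 1.69 = 30.3, so 31 (32 with the t distribution).

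The stated 64 per arm is not reproduced; 64 matches the total. That is a separate discrepancy, but it matters here because 64 per arm leaves slack. An adjusted analysis at 64 per arm has 99% power at SD 13% and 96% at SD 15%. The drop-out step does reproduce: 64 / 0.8 = 80.

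**2. Losing the baseline adjustment.** The correlation r between baseline and week-26 time in range is not in the protocol; 0.5, 0.6 and 0.7 are assumed. Each SD is treated as the baseline-adjusted SD.

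- Unadjusted SD = adjusted SD / √(1 − r²)
- Rank-sum efficiency relative to the t-test under normality = 0.955, so effective n = 64 × 0.955 = 61.1 per arm
- Sample-size inflation = 1 / [(1 − r²) × 0.955]
- Power from a two-sample t-test for a 10-point difference

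| | r = 0.5 | r = 0.6 | r = 0.7 | Adjusted |
|---|---|---|---|---|
| Inflation | 1.40 | 1.64 | 2.05 | 1 |
| Unadjusted SD (from 13) | 15.0 | 16.2 | 18.2 | 13 |
| Power, SD 13% | 95% | 92% | 85% | 99% |
| Unadjusted SD (from 15) | 17.3 | 18.8 | 21.0 | 15 |
| Power, SD 15% | 89% | 83% | 74% | 96% |

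**3. When the fallback would actually run.** The factor 0.955 applies to normal data, whereas the rank-sum test is invoked for non-normal data. Simulations with skewed or heavy-tailed errors (such as gamma with shape 2, or t with 4 degrees of freedom), 64 per arm and a 10-point shift, gave roughly:

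- SD 15%: 93–95 / 88–90 / 77–83%, against 95–96% for the adjusted analysis
- SD 13%: 98 / 95–96 / 87–91%, against about 99%

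The loss is smaller, but it remains at the higher correlations. ANCOVA loses almost nothing under these errors.

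**4. Does the rank-sum test compare medians?** Two distributions with the same median but mirror-image exponential skew, 64 per arm, 4,000 runs: the rank-sum test rejects in 47% of runs at the nominal 5% level. As a test of equal medians it would reject in 5%.

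**5. Omitted minimisation factors.** Suppose age and diabetes duration explain 5% or 10% of the residual variance (assumed).

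- Interval width ratio: √(1/0.95) = 1.026; √(1/0.90) = 1.054
- Actual size of the nominal 5% test: 2 × P(Z > 1.96 × 1.026) = 4.4%; 2 × P(Z > 1.96 × 1.054) = 3.9%

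A simulation of minimisation on all four factors (64 per arm, biased coin 0.8, adjusted SD 13, r = 0.6, 1,500 runs per setting) gave:

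| | Baseline + site | All four factors |
|---|---|---|
| Type I error, age and duration each worth 8 points | 3.3% | 5.1% |
| Type I error, neither prognostic | 6.2% | 6.4% |
| Power for 5 points, each worth 8 points | 58% | 67% |

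The Monte Carlo standard error of the type I figures is about 0.6 points. The 8-point effects are assumed and large.

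**The case against.** **The planned N absorbs most of the loss.** This stands in part. At SD 13%, the value the protocol plans with, the unadjusted rank test keeps about 85% power or more up to r of about 0.7. At SD 15% it does so only to just under 0.6.

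**The protocol does offer a mean comparison.** This also stands in part. Least-squares mean differences are promised, and the bootstrap for skewed data concerns arithmetic means. So it would go too far to say that no percentage-point estimate survives. But no baseline or site adjustment is stated for the bootstrap, and it is added to the rank-sum test rather than replacing it.

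**The covariate omission is minor.** Agreed. It errs on the conservative side, the most relevant baseline variable is in the model, and the documents do not say how prognostic age and duration are.

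Three stronger readings are tempting and are not supported:

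- *The test would be picked after seeing unblinded data.* The protocol does not say when, on what values or under what blinding normality is judged. Those details, and the order of precedence among the methods, are commonly left to a statistical analysis plan, so their absence is not held against the protocol.
- *The sample size rests explicitly on a baseline-adjusted SD that the fallback discards.* Only the 15% is described as baseline-adjusted. The 13% actually used carries no such label, and 64 per arm does not follow from it.
- *The switch or the omitted factors inflate type I error.* Omission makes the test conservative. With normal outcomes and an assumed Shapiro–Wilk trigger, the two-stage rule rejected at nearly the same rate as the ANCOVA alone (6.0% against 6.2% with no prognostic effect; 3.3% for both with 8-point effects).

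**Conclusion.** The concern holds in a limited form. Some of it rests on the text alone: the protocol lets the observed distribution decide which test judges the primary endpoint, the named fallback drops the baseline and site adjustment and the percentage-point scale, and its description as a test of medians is wrong without a shift assumption.

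The power loss is conditional on the unstated correlation. At SD 15% and r = 0.7 it is about 22 percentage points in normal theory (96% to 74%), and roughly 12 to 19 points with the skewed or heavy-tailed errors tried. At SD 13% and r = 0.5 it is only a few points (99% to 95%).

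The missing age and duration terms are secondary: intervals 2.6–5.4% too wide if the two explain 5–10% of residual variance, and no effect if they are not prognostic. This should be corrected, but it does not by itself put the trial's conclusion in doubt.

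**What to change.** In section 7.3, state one primary analysis that applies whatever the distribution: ANCOVA of % time in range at 23–26 weeks on treatment, with continuous baseline time in range, site, age and diabetes duration as covariates, reporting the adjusted mean difference with its 95% confidence interval.

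Make a bootstrap or heteroscedasticity-robust interval for that same adjusted difference the sensitivity analysis for non-normality. Delete the distribution-triggered switch and the statement that the rank-sum test compares medians. If a rank-based analysis is wanted, label it supportive and preferably adjust it for baseline, for example as a rank ANCOVA. Carry the change through to the secondary CGM percentages, which inherit the same rule.

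The cost is a wording change and two degrees of freedom. Date of birth and date of diagnosis are already recorded at Visit 1, and age and duration are already used in allocation.
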